## 11.0 Data and Specimen Management

#### 11.1 Data Analysis Plan

The primary analysis will be a mixed model repeated measures ANCOVA adjusting for baseline differences in dependent measures, sex and race. Missing data will be imputed by MMRM. We would also examine some variables categorically.

Assumptions for the power analysis included random assignment into one group receiving placebo and one JNJ-18038683. The cognitive battery, as the primary instrument, will be collected at baseline and at end point (8 weeks). Using repeated measure ANCOVA, the time average difference in the response variable will be compared between groups to detect treatment difference. Based on Javitt et al, 2012, we assume the mean baseline verbal learning score will be 36.2, SD 9.4 for both groups. We are assuming the placebo group will show no improvement while the treatment group will improve a mean of 5 points, a medium effect. We assume the correlation coefficient of repeated observation to be 0.5 and the covariance structure to be compound symmetry. The power calculation was conducted with alpha level of 0.05 using one-sided and two-sided tests. Full results are available upon request. With a one sided test, 33 individuals per group are required assuming 5 points improvement of the treatment group compared to the placebo for the desired power of 80% with alpha level of 0.05. We plan to recruit 36 per group to account for drop outs. In the two sided test the sample size per group is 42.

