Secondary analyses related to efficacy:

The secondary analyses regarding change in verbal fluency test scores will include identification of patients in each arm who improved in verbal fluency scores. The analysis plan includes exploring the effect of concomitant meds, gender or race that might contribute to treatment response. For this purpose, improvement in verbal fluency can be grouped as a dichotomous response and used as a dependent variable in a logistic regression model. The usual method of grouping will be improvement of ≥0.5 SD from the baseline scores. Using this model, the odds of improvement in verbal fluency can be compared in the active treatment group against the placebo group. In this model, the variables, age, gender, lab values and presence/absence of concomitant meds, baseline MADRS total score, YMRS and Clinical Global Severity score mania or depression severity may influence performance on cognitive testing and will be tested as potential covariates using one or few covariates at a time due to sample size restrictions.

Additional secondary analyses will study the effect of treatment group on other cognitive and behavioral measures including: 1) Digital Symbol Task, 2) Brown-Peterson Consonant Trigram Memory Task, 3) WISC-III Mazes; 4) Wisconsin Card Sorting Test; 5) MADRS total score,6) YMRS, and 7) Clinical Global Severity score using a mixed model repeated measure ANCOVA as described above. If indicated, variables such as age, gender, concomitant meds, will be examined, as will be done for the primary outcome measure.

Adverse Events:

A tabular summary of all anticipated and unanticipated serious or non-serious adverse events will be presented, including drop-outs due to any side effects or safety reasons. For each serious or other adverse events, the summary includes the adverse event term, affected organ system, number of participants at risk, and number of participants affected, by the study arm or comparison group. Using appropriate parametric or non-parametric methods, each type of adverse event will be compared between groups. All adverse events, e.g. development of suicidal ideation or behaviors or switch to mania/hypomania, will be examined thoroughly for impact on primary and secondary outcome measures. We will assess group differences, excluding subjects without these two side effects.

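### The SAP looks for predictors of treatment response with a yes/no 0.5 SD label, no listed baseline cognitive score and no treatment-by-factor term; a baseline-adjusted continuous model would serve better

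*SAP*

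**What the plan says.** The SAP section on secondary efficacy analyses plans the "identification of patients in each arm who improved in verbal fluency scores". It then says that "improvement in verbal fluency can be grouped as a dichotomous response and used as a dependent variable in a logistic regression model", and sets the cut: "The usual method of grouping will be improvement of ≥0.5 SD from the baseline scores". The stated purpose is to see whether concomitant medication, gender or race plays a part in response. The same model also compares the odds of improvement between drug and placebo. Its candidate covariates are age, gender, laboratory values, concomitant medication and baseline MADRS, YMRS and global severity, entered one or a few at a time because the sample is small. The baseline cognitive score is not on that list, and no interaction between treatment and any factor is mentioned.

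The SAP does not say whose SD defines the cut, or whether the cut applies to each test or to a composite. It gives no basis for 0.5 SD and no expected placebo rate.

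The only planning figures for a cognitive score are in Protocol section 11.1. For the starting level, "we assume the mean baseline verbal learning score will be 36.2, SD 9.4 for both groups". As to change, the protocol expects none on placebo and a mean gain of 5 points on drug. On the link between visits it states: "We assume the correlation coefficient of repeated observation to be 0.5", with compound symmetry.

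**The concern.** There are three separate weaknesses.

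- **The label is easy to earn by chance variation.** If scores move between visits as much as the planning correlation implies, a gain of half a baseline SD is common in patients whose group shows no mean change.
- **The label depends strongly on the starting score.** A patient who happens to test low at baseline tends to score higher at Week 8. Without the baseline cognitive score in the model, a factor that goes with a temporarily low baseline can appear to predict response. The SAP itself expects baseline mood state to affect test performance, so such factors are plausible here.
- **The model does not ask the stated question.** A covariate main effect shows who gains in either arm. Which patients gain more on drug than on placebo is a treatment-by-factor question.

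In addition, dichotomising a continuous score in a trial of 60 patients gives up power. At stake is the credibility of any statement about who responds to the drug, which could steer the design of a later study.

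**Working it through.** **Inputs.** From Protocol section 11.1: SD 9.4 in both groups, correlation 0.5, compound symmetry (equal SD at both visits), mean change 0 on placebo and 5 points on drug. From Protocol section 22.0: 30 randomised per arm. From the SAP: a cut of 0.5 SD, read here as 0.5 × the SD of baseline scores = 0.5 × 9.4 = 4.7 points. Scores are taken as normal.

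**1. The plan's own figure.** For a time-averaged difference over two time points, the effective SD is 9.4 × √((1 + 0.5)/2) = 8.14. One-sided at 0.05 with 80% power: n = 2 × (8.14 × (1.645 + 0.842)/5)² = 32.8, so 33 per group; power at 33 is 0.802. Two-sided: 41.6, so 42 per group. Both agree with the protocol, so the inputs are read as intended.

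**2. Chance of the label with no mean change.** SD of change = 9.4 × √(2 × (1 − 0.5)) = 9.4 points. P(gain ≥ 4.7) = 1 − Φ(4.7/9.4) = 1 − Φ(0.5) = 30.9%, or 0.309 × 30 ≈ 9 placebo patients. A simulation of one million pairs gave 30.85%.

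The correlation drives this figure. Values other than 0.5 are assumptions:

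- 0.5: 30.9%
- 0.7: 25.9%
- 0.8: 21.5%
- 0.9: 13.2%

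An assumed 2-point practice gain at correlation 0.5 would raise the rate to 1 − Φ(2.7/9.4) = 38.7%.

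**3. Dependence on starting score.** In baseline SD units with correlation 0.5 and no mean change, a patient starting at x has an expected gain of −0.5x, with residual SD √(1 − 0.25) = 0.866.

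- Start 1 SD below the mean: expected gain +0.5, so P = 1 − Φ((0.5 − 0.5)/0.866) = 50%.
- Start 1 SD above the mean: expected gain −0.5, so P = 1 − Φ((0.5 + 0.5)/0.866) = 1 − Φ(1.155) = 12%.

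Starting score alone thus produces about a fourfold difference in apparent response.

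**4. Power for the overall treatment effect, 30 per arm, two-sided 0.05.**

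- Responder rate on drug: 1 − Φ((4.7 − 5)/9.4) = 51.3%, against 30.9% on placebo. Normal-approximation power is about 36%; about 90 per arm would be needed for 80%.
- ANCOVA on Week 8: residual SD 9.4 × √(1 − 0.5²) = 8.14; SE = 8.14 × √(2/30) = 2.10; power = Φ(5/2.10 − 1.96) ≈ 66%.

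**5. Power for an interaction on the continuous score.** With an evenly split factor, SE = 2 × 2.10 = 4.20. For a 5-point interaction, power = Φ(5/4.20 − 1.96) ≈ 22%, and it is lower with an uneven split.

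**The case against.** Several objections carry weight.

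- **31% is not a property of the rule.** A reader might infer that nearly a third of placebo patients will be labelled improved through measurement error alone. The documents do not support that. The correlation of 0.5 is a planning value for a verbal learning score, not a reliability estimate. Over eight weeks it mixes measurement error with real individual fluctuation. The SAP applies the cut to an outcome that it calls verbal fluency, assessed with four tests, and gives no SD or correlation for it. At an assumed correlation of 0.9 the rate is 13%.
- **The between-arm comparison is sound.** A reader might also infer that the responder odds ratio is biased. It is not: chance labelling affects both randomised arms, so it does not by itself inflate type I error. The placebo arm supplies its own benchmark.
- **Continuous analysis already exists.** The SAP's primary analysis is ANCOVA on the Week 8 outcome with baseline as covariate, and age and mood measures are examined in it. The protocol's primary model adjusts for sex and race. The information loss belongs to one secondary model, worded permissively. Even so, no treatment-by-factor term is stated for the existing models, so they do not answer the question posed here.
- **The 36% against 66% contrast concerns the overall treatment effect.** It does not show that the search for modifiers becomes well powered; at about 22% for a 5-point interaction it remains weak.
- **Not every linked factor misleads.** One that lowers scores equally at both visits creates no regression to the mean. The risk lies with factors tied to a temporarily low baseline.

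**Conclusion.** The point holds as a limited one. The model meant to show what contributes to response uses a label that, on the protocol's planning inputs, about 31% of placebo patients would receive (13% to 26% at assumed correlations of 0.9 to 0.7). The chance of the label runs from about 50% to 12% across starting scores 1 SD below and above the mean. The model does not list the baseline score that would adjust for this, and it has no term that separates response to drug from gain in either arm. Dichotomising also costs power for the overall effect.

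The figures assume normal scores, equal SDs, no mean placebo change, the baseline-SD reading of the cut, and that the verbal learning inputs carry over to the SAP's outcome. The weaknesses in the model's structure do not depend on the exact correlation. The analysis is secondary and the primary result does not rest on it, so this is an inexpensive improvement and not a threat to the trial.

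**What to change.** In the SAP's secondary efficacy section:

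1. Run the exploration on the continuous Week 8 score with the SAP's own ANCOVA: baseline score, treatment, the factor, and one treatment-by-factor term at a time. Label it exploratory, report each interaction with its confidence interval, and acknowledge the low power (about 22% for a 5-point interaction with an evenly split factor).
2. Keep the proportion gaining at least 0.5 SD as a by-arm descriptive summary, with the between-arm difference and its confidence interval. Define the SD as the pooled baseline SD, and say whether the cut applies per test or to a composite.
3. Use the observed placebo proportion as the benchmark. Do not write a fixed 31% into the SAP.
4. Do not describe individual patients as truly improved on this rule.
5. If the logistic model is retained, add the baseline cognitive score as a covariate.

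The cost is a wording change, with no new data or visits. The downside is that odds ratios of response are no longer the main output of this secondary analysis. The change does not cure the small sample: modifier findings would remain hypothesis-generating.

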#### 9.1 Outcome Measures:

- A) Comprehensive cognition battery (measuring executive functioning, speed of processing, attention/vigilance, working memory, verbal learning, visual learning, reasoning and problem solving)
- B) Montgomery Asberg Depression Rating scale
- C) Young Mania Rating Scale
- D) Clinical Global Impression BP
- E) Columbia Suicide Severity Rating Scale
- F) AIMS scale for tardive dyskinesia
- G) Specific Level of Functioning
- H) Weight, height, waist circumference, triglycerides, FBS, LFTs

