#### 9.3.2 Special Warnings and Precautions for Use

JNJ-18038683 is an investigational drug, with safety data available from nonclinical animal studies, as well as single and multiple dose clinical studies in healthy volunteers.

All individuals should be closely monitored by means of adverse events, vital signs, ECGs, and clinical laboratory safety tests of blood and urine.

The liver, lung, prostate, mammary gland, hematologic system, and thymus in rats (mainly at high dose), and the hematologic system and spleen in dogs, were identified as potential target organs for JNJ-18038683 in repeat-dose oral toxicity studies (see Other Effects in Investigator Brochure). Female animals appeared to be more susceptible than males.

Thus far in clinical trials, there have been no laboratory abnormalities of concern, but the following safety tests should be monitored:

- Hematologic parameters: red blood cell (RBC), hemoglobin, hematocrit, unconjugated bilirubin, reticulocyte, and platelet counts;
- Liver function: aspartate transaminase (AST), alanine transaminase (ALT), gamma glutamyltransferase (GGT), prothrombin time, total bilirubin, lactic dehydrogenase, serum albumin, and protein.

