#### 9.4.9 Vital Signs

Arterial systolic and diastolic blood pressure and radial artery pulse rate will be measured while the patient is seated at the scheduled visits designated in the Schedule of Events in Appendix 1.

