#### 9.4.14 Laboratory Test Assessments

Northwestern Medicine Laboratory and South Bend Medical Foundation will be used for analysis of fasting lab assessments required during the study. Blood will be drawn from each patient at the screening visit, and at end of study as noted in the study Schedule of Events in Appendix 1. The tests will include: Chemistry panels; Hematologic parameters: red blood cell (RBC), hemoglobin, hematocrit, unconjugated bilirubin, reticulocyte, and platelet counts; Liver function: aspartate transaminase (AST), alanine transaminase (ALT), gamma glutamyltransferase (GGT), prothrombin time, total bilirubin, lactic dehydrogenase, albumin, protein, creatinine. A urine drug screen (UDS) will be obtained at screening only. In women of childbearing potential, serum pregnancy testing will occur at screening; urine pregnancy will occur at study baseline.

Note: At screening and throughout study participation, a positive UDS is not necessarily exclusionary and/or may not require a subject be withdrawn from the study. This decision will be per the discretion of the principal investigator.

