Data Analysis Plan for Northwestern- Janssen R&D Collaboration Study

Protocol Title: Testing the ability of JNJ-18038683, a selective serotonin (5-HT)7 antagonist, to

improve cognition and reduce residual depressive symptoms in stable bipolar patients

Protocol Identifier Number: 18038683BCD2001

Northwestern University IRB Number: STU00200919-MOD0042

Version: 1.13

Date: 08.04.2021

Goals:

The goals of this study are to evaluate the efficacy of JNJ-18038683 in an 8-week trial to ameliorate the cognitive deficit and reduce residual depressive symptoms in 60 stable bipolar outpatients receiving treatment for depression. JNJ-18038683 will be studied and compared with placebo as adjunctive treatment to standard pharmacologic treatment for bipolar disorder. Sixty patients will be enrolled and randomized with a 1:1 ratio to one dose of JNJ-18038683 or placebo providing 30 subjects for each treatment arm. The initial intention was to follow stratified randomization based on the presence/absence of atypical APDs with 5-HT7 antagonism so that there is a balance in the assignment of active treatment and placebo in individuals who are and are not, receiving atypical APDs with 5-HT7 antagonism. However, due to recruitment difficulties, the stratified randomization method was not able to be followed as anticipated and was amended.

Assessments and Events:

Demographics, medical history, physical examination, serum pregnancy test, urine drug test, SCID-I diagnosis, and screening neurocognitive assessments will be done only during the screening visit. Urine pregnancy testing is performed at the baseline visit.

Table 1: Assessments completed during the screening visit only

Event /Assessment	Screen
Medical History & Demographics	X
Physical Examination	X
Serum Pregnancy Test	X
Urine Drug Screen	X
Inclusion/Exclusion Criteria	X
SCID-I	X
Screening neurocognitive assessments	X

Neurocognitive battery will be the primary measure of interest and evaluated at baseline and 8 weeks. The clinical global severity scores (CGI-BP), Young Mania Rating (YMRS), Scale for Tardive Dyskinesia (AIMS), Montgomery Asberg Depression Rating Scale (MADRS), Electrocardiogram and Clinical Safety Laboratory Tests will be collected at screening or baseline, and at 4 and 8 weeks. A measure of functional ability (SLOF) also will be assessed at baseline and 8 weeks. The schedule of these assessments is listed in table 2.

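### Hematology and liver safety tests have no planned by-arm summary: the SAP uses lab values only as a candidate efficacy covariate and analyses safety through adverse events alone

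*SAP*

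**What the plan says.** **Why the tests are taken.** Protocol 9.3.2 reports repeat-dose animal studies in which the liver and the hematologic system were among the potential target organs. It qualifies the rat findings as mainly at high dose. It adds "Female animals appeared to be more susceptible than males". Of the clinical experience so far it says "there have been no laboratory abnormalities of concern, but the following safety tests should be monitored", and then lists hematologic and liver tests. Item H of section 9.1 makes the following outcome measures: "Weight, height, waist circumference, triglycerides, FBS, LFTs".

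**When they are taken.** The SAP (Assessments and Events) says "Electrocardiogram and Clinical Safety Laboratory Tests will be collected at screening or baseline, and at 4 and 8 weeks", and SAP Table 2 and both protocol schedules (section 7.0 and Appendix 1) agree. Protocol 9.4.14 differs: "Blood will be drawn from each patient at the screening visit, and at end of study as noted in the study Schedule of Events".

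**What is done with them.** Under its secondary efficacy analyses, the SAP offers "the variables, age, gender, lab values and presence/absence of concomitant meds", with baseline symptom scores, as potential covariates in the logistic model for verbal fluency response. Its Adverse Events section tabulates adverse events by term, organ system and arm, and compares each type between groups. It contains no laboratory analysis.

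**Vital signs.** Protocol 9.4.9 says "Arterial systolic and diastolic blood pressure and radial artery pulse rate will be measured while the patient is seated". SAP Table 3 schedules vital signs at seven visits. No summary is planned.

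**The concern.** Protocol 9.3.2 asks for close monitoring through four channels: adverse events, vital signs, ECGs and laboratory tests. The SAP analyses one of them. Liver tests, an outcome measure in protocol 9.1, are never compared between the arms. They enter the plan only as possible explanatory variables for a cognitive response.

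At stake is what the trial can say about safety. A drug-related shift in, say, a transaminase, hemoglobin or the platelet count could be present in the collected data and appear in no planned table if individual values were not recorded as adverse events. If such tables are produced later without a plan, the tests, visits and cut-offs may be chosen with the results in view.

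There is a second, smaller problem. The SAP does not say which visit's lab values may enter the logistic model. Week 4 or Week 8 values could be affected by treatment, and adjusting for them could distort the treatment odds ratio.

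**Working it through.** The plan gives no figure for laboratory data, so there is none to reproduce. The check has two parts: a side-by-side reading, and a rough look at what 30 per arm could show.

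**1. Every place where a laboratory analysis could be planned**

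| Place | Content | By-arm lab analysis? |
|---|---|---|
| Protocol 8.0 | Tolerability: weight, BMI, waist circumference, movement scales | No |
| Protocol 9.1 | Liver tests, triglycerides and fasting blood sugar listed as outcome measures | Listed, no analysis given |
| Protocol 9.3.2 | Tests to monitor | No |
| Protocol 9.4.14 | Tests and timing of draws | No |
| Protocol 11.1 | Some variables, unnamed, to be examined categorically | Not specified |
| SAP, baseline comparison of arms | Efficacy measures, psychopathology, demographics, suicide status | No |
| SAP, secondary efficacy | Lab values as candidate covariates | No |
| SAP, Adverse Events | Adverse-event tables and comparisons | Only for results recorded as adverse events |

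The last row matters. Protocol 9.3.5.1 says an adverse event can be an abnormal laboratory finding, and 9.4.11 requires all observed adverse events to be recorded. Laboratory data therefore have one route to a by-arm comparison. That route leaves judgement over what counts as an event, and it cannot show a shift within the reference range. For ECGs, 9.4.10 requires clinically significant changes to be recorded as adverse events; 9.4.14 has no matching rule for laboratory results.

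**2. What by-arm summaries could show**

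Inputs: 30 per arm (protocol 22.0); correlation between screening and later value r = 0.5. Protocol 11.1 uses 0.5 for the cognitive score; applying it to a lab value is an assumption. No dropout is assumed.

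- Standard error of a screening-adjusted difference, in SD units: sqrt((2/30) × (1 − r²)) = sqrt(0.0667 × 0.75) = 0.224.
- 95% half-width with 57 degrees of freedom: 2.002 × 0.224 = 0.448, about 0.45 SD. With r = 0.3 it is 0.49 SD; with r = 0.7 it is 0.37 SD.
- Unadjusted difference detectable with 80% power, two-sided 0.05: (1.960 + 0.842) × sqrt(2/30) = 0.72 SD.
- If none of 30 active patients has a given abnormality, the one-sided 95% upper limit for its rate is 1 − 0.05^(1/30) = 9.5%.

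Mean shifts can be described with moderate precision. Uncommon abnormalities cannot be excluded. Both results favor descriptive tables over formal tests.

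**3. Number of estimates**

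Protocol 9.3.2 lists 6 hematologic and 8 liver items, 14 in all. At two post-screening visits that is 14 × 2 = 28 intervals. With no drug effect, 28 × 0.05 = 1.4 of them would be expected to exclude zero.

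**The case against.** The strongest case against runs as follows. The tests are there for monitoring individual patients. The animal findings were mainly at high dose in rats, and 9.3.2 reports no laboratory abnormality of concern in clinical trials so far. An abnormality that matters should be recorded as an adverse event, and those are compared by arm. Nothing prevents a laboratory table from being produced, and 28 intervals in a 60-patient trial will bring chance findings.

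Much of this stands. It limits the point to shifts and values not recorded as adverse events, and it is why the tables should be descriptive. It does not remove the gap: monitoring individual patients does not compare the arms, and neither document promises such a table.

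A reader might infer more than the documents support:

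- **That a liver or blood signal would go unreported.** The documents show only that there is no planned report of values outside the adverse-event tables.
- **That one can state how likely the adverse-event route is to miss a shift.** The answer depends on a recording threshold that the documents do not give. For an assumed 0.75 SD shift in one test among 30 active patients, the chance of no recorded event is 69% with a 3 SD threshold and one draw, 50% with the same threshold and two draws correlated 0.5, and 3.5% with a 2 SD threshold and one draw. No figure in that range can be defended.
- **That all the named organs lack a planned analysis of their tests.** Section 9.3.2 also names lung, prostate, mammary gland, thymus and spleen, but lists only hematologic and liver tests.
- **That the 2.5 × ULN limit for ALT and AST is a ready on-treatment category.** In protocol 3.2 it is an entry exclusion only.

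The case for vital signs is weaker. It rests on their being listed for monitoring and on palpitations, a reported symptom, being more frequent on the drug in the trial described in 9.3.

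**Conclusion.** The point holds in this limited form. The hematology and liver tests in protocol 9.3.2, and the liver tests listed as outcomes in 9.1, have no planned by-arm summary in either document. The SAP's only stated use of lab values is as candidate efficacy covariates. Results recorded as adverse events are covered; group-level shifts and other values are not.

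The omission is established by reading and needs no numerical assumption. The precision figure (about ±0.45 SD) rests on 30 completers per arm and a correlation of 0.5. It shows only that the summary would be informative for moderate shifts. The primary efficacy result is unaffected. What changes is how much the trial can say about laboratory safety.

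The number of post-screening draws is unsettled: one under the wording of 9.4.14, two under the schedules and the SAP. These passages must be reconciled.

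**What to change.** 1. In the SAP's safety section, add a descriptive table by arm for each hematology and liver test in protocol 9.3.2, at each scheduled post-screening visit. Give the value, the change from screening, and a shift table against the laboratory's reference range. Give the screening-adjusted difference with a 95% confidence interval, on the log scale for skewed enzymes and bilirubin, and label it descriptive.
2. Add a descriptive by-arm summary of systolic and diastolic pressure and pulse at each visit.
3. If lab values remain candidate covariates in the logistic model, restrict them to screening values.
4. Reconcile protocol 9.4.14 with section 7.0, Appendix 1 and SAP Table 2 on whether blood is drawn at Day 28, so that the visits in the table are unambiguous.

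The cost is SAP wording and some extra tables; the data are already scheduled, subject to item 4. The downside is more safety estimates, some of which will differ by chance, hence the descriptive label. The SAP is dated 2021 and describes treatment in the past tense, and the documents do not say whether the data have been unblinded. If they have, the tables are still worth adding, marked as specified after unblinding.

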#### 9.3 Adverse Events

In a 7 week, randomized, placebo controlled trial comparing JNJ-18038683 with placebo and escitalopram (an active comparator), a total of 6 serious adverse events were reported during the study (placebo group: spontaneous abortion and suicidal ideation; escitalopram group: spontaneous abortion, suicidal ideation, suicide attempt, and chest discomfort). A total of 10 individuals (3 in the placebo group, 4 in the JNJ-18038683 group, and 3 in the escitalopram group) were withdrawn from the study prematurely due to adverse events. The 4 events leading to drop out of individuals on JNJ-18038683 were one instance each of the following: bundle branch block, panic attack, upper respiratory infection, and insomnia.

Only 3 individuals receiving the 20-mg dose of JNJ 18038683 required dose reductions at any point during the study.

Adverse events that were reported in more than 5% of individuals in any treatment group included headache, nausea, nasopharyngitis, insomnia, somnolence, dyspepsia, dizziness, dry mouth, constipation, diarrhea, vomiting, back pain, upper respiratory tract infection, palpitations, and fatigue. The treatment-emergent adverse events that were reported more frequently in the JNJ 18038683 group compared with the placebo or escitalopram groups included dyspepsia, constipation, upper respiratory tract infection, and palpitations.

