#### 22.0 Local Number of Individuals

After screening for eligibility and providing written informed consent, 60 stable outpatients, who may have mild-moderate depressive symptoms, will be randomized to receive adjunctive treatment with either JNJ-18038683 or placebo.

We propose to study a total of 60 randomized participants, 30 receiving JNJ-18038683 and 30 randomized to placebo.

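### The SAP compares each adverse event type between arms of 30 by an unnamed test, with no effect estimate or interval; non-significant results could not support a claim of no excess harm.

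*SAP*

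**What the plan says.** The SAP plans a "1:1 ratio to one dose of JNJ-18038683 or placebo providing 30 subjects for each treatment arm". Protocol section 22.0 gives the same numbers: "30 receiving JNJ-18038683 and 30 randomized to placebo".

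The SAP's Adverse Events section does two things. First, it sets out a descriptive table giving, for each event term and organ system, the "number of participants at risk, and number of participants affected, by the study arm or comparison group", and it also lists drop-outs for side effects or safety reasons. Second, it adds a between-arm comparison: "Using appropriate parametric or non-parametric methods, each type of adverse event will be compared between groups".

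For that comparison it gives no test, significance level, sidedness, effect measure, confidence interval, multiplicity rule or rule for interpreting a non-significant result. The only significance level in either document is in Protocol section 11.1 and belongs to the efficacy sample size: "The power calculation was conducted with alpha level of 0.05 using one-sided and two-sided tests".

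Protocol section 9.3 gives limited information on event rates, from an earlier trial of the drug: "Adverse events that were reported in more than 5% of individuals in any treatment group included headache, nausea, nasopharyngitis, insomnia, somnolence", and further terms to a total of 15. It also names four events that were more frequent on the drug (dyspepsia, constipation, upper respiratory tract infection and palpitations). It gives no rate for any single event.

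**The concern.** The data for each event type are patients affected out of patients at risk in two arms of about 30. With counts that small, two problems follow.

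First, the usual candidate tests disagree near the 0.05 line. Leaving the test open means that the same table can be called significant or not according to a choice made after the data are seen.

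Second, power for moderate differences is low, so a non-significant result says little about whether the drug causes the event. The unnamed test is the only between-arm comparison planned for adverse events. With no risk difference or interval beside it, a reader has no direct statement of how large an excess the trial leaves open. That matters for the events the protocol already lists as more frequent on this drug. In the other direction, testing many event types with no multiplicity rule invites chance positives.

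**Working it through.** **The plan's own figure.** The documents give no power or detectable difference for adverse events. Their only calculation is for efficacy. Its inputs are in Protocol section 11.1. For the effect: "We are assuming the placebo group will show no improvement while the treatment group will improve a mean of 5 points, a medium effect". For the spread, an SD of 9.4 in each arm, with a correlation of 0.5 between two time points.

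- Time-averaged SD = 9.4 × √((1 + 0.5)/2) = 8.141.
- n per group = 2 × (z_α + z_β)² × 8.141² / 5². This gives 33 one-sided (power 0.802) and 42 two-sided (power 0.804).

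Both match the protocol, and neither bears on adverse events.

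**Inputs for the check.** 30 per arm is from the documents. Two-sided α = 0.05 is an assumption. The true event rates in step 3 are also assumptions, because the protocol gives only a 5% threshold.

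**Step 1: one table, several tests (5/30 against 0/30).**

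- Fisher, one tail: C(30,5)/C(60,5) = 142,506/5,461,512 = 0.0261. Two-sided: 2 × 0.0261 = 0.052.
- Uncorrected chi-square: 60 × (5×30 − 25×0)² / (30×30×5×55) = 5.45, p = 0.020.
- Yates-corrected chi-square: p = 0.062.
- Barnard: p = 0.022. Boschloo: p = 0.027.

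Two of the five tests are above 0.05 and three are below. Fisher is a natural choice because the expected count is 5/2 = 2.5 per arm, but the SAP does not commit to it. Under two-sided Fisher the smallest significant split against zero is 6/30 against 0/30: 2 × C(30,6)/C(60,6) = 2 × 593,775/50,063,860 = 0.024. The Fisher value for 5 against 0 stays just above 0.05 at the arm sizes checked from 25 to 36 (0.0502 to 0.0539).

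**Step 2: what zero events excludes.** Exact two-sided 95% upper limit for 0/30: 1 − 0.025^(1/30) = 11.6%.

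**Step 3: power at 30 per arm.** Power is the sum, over all pairs of counts (x, y) for which p < 0.05, of Bin(x; 30, p₁) × Bin(y; 30, p₂).

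| Assumed true rates | Fisher | Uncorrected chi-square |
|---|---|---|
| 10% v 5% | 2% | 11% |
| 15% v 5% | 9% | 26% |
| 20% v 5% | 24% | 45% |
| 30% v 5% | 63% | 78% |

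For scale, 80% power at 20% v 5% by the normal approximation needs [1.960√(2×0.125×0.875) + 0.842√(0.2×0.8 + 0.05×0.95)]² / 0.15² = 75.1, so 76 per arm.

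**Step 4: multiplicity.** For the 15 terms listed in Protocol section 9.3, 1 − 0.95¹⁵ = 0.54. This treats the tests as independent and each at its full 5% level. Fisher is conservative for rare events, so the true figure would be lower.

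**Step 5: what an interval would show (Newcombe, 95%).**

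- 5/30 v 0/30: +16.7 points (2.0 to 33.6).
- 2/30 v 2/30: 0 points (−15.4 to +15.4).

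The second line states what a non-significant p-value leaves out: equal counts still leave an excess of about 15 points open.

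**The case against.** The strongest reply is that the SAP never says that a non-significant comparison will be reported as no difference, or that any safety conclusion will rest on p-values. A reader might infer this from the comparison sentence, but it would be a prediction about the write-up, and the documents do not support it. This part of the reply stands.

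Nor would a p-value be the only information by arm. The planned table gives numerator and denominator for every event, so a 5 against 0 imbalance would be visible and a risk difference could be worked out from it. That stands too. What is missing is a planned estimate with its uncertainty.

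Three further limits are fair. It is tempting to say flatly that 5 against 0 is non-significant, but that holds only under Fisher or Yates. It is also tempting to say that parametric methods cannot apply to such counts; that is too broad, since a two-proportion comparison and logistic regression are parametric, and the SAP's wording is vague rather than wrong. And the earlier trial's named events come without rates or tests, so they do not establish a real excess on the drug.

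Finally, safety is not the powered objective, and most trials of 60 patients could not detect moderate differences in adverse events. That is true. It is also a reason to estimate rather than test.

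**Conclusion.** The point holds in a limited form. The SAP commits to comparing every adverse event type at about 30 per arm without choosing a method or planning an estimate, and the choice of test can reverse the result for a table such as 5 against 0 (p from 0.020 to 0.062). Power for moderate differences is low under either test examined: at most 45% for 20% against 5%, and at most 26% for 15% against 5%. It becomes moderate only for large differences (63% or 78% for 30% against 5%). Non-significant p-values from these comparisons therefore could not support a conclusion of no excess harm.

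This rests on an assumed two-sided 0.05 level, illustrative event rates, and 30 analysed patients per arm. It does not show that the investigators intend to claim absence of harm, or that imbalances would be hidden. It is a minor point about reporting, but worth changing because it affects what the trial can say about harms.

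**What to change.** Keep the planned by-arm table. Replace the comparison sentence with a commitment to report the risk difference and a 95% confidence interval for each adverse event type, for serious adverse events and for discontinuations due to adverse events. Name one exact or score-based interval method in advance, because the choice matters at these counts: the Newcombe interval for 5 against 0 excludes zero, while two-sided Fisher gives p = 0.052. If p-values are kept, name the test, label them descriptive and unadjusted for multiplicity, and state that a non-significant comparison is not evidence of no difference.

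The cost is a short SAP edit and slightly more table programming. No new data or design change is needed. What is given up is formal per-event testing, which at this size would have told the reader little.
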